# 1. LIST OF ABBREVIATIONS AND DEFINITIONS

Abbreviation	Abbreviated Defined	
AACE	American Association of Clinical Endocrinologists	
ADA	American Diabetes Association	
AAE	Anticipated Adverse Event	
ADE	Adverse Device Effect	
AE	Adverse Event	
AESIs	Adverse Events of Special Interest	
ALP	Alkaline Phosphatase	
ALT	Alanine Aminotransferase	
ASADE	Anticipated Serious Adverse Device Effect	
AST	Aspartate Aminotransferase	
BMI	Body Mass Index	
BUN	Blood Urea Nitrogen	
CEC	Clinical Events Committee	
CFR	Code of Federal	
CFK	Regulations	
CGM	Continuous Glucose Monitoring	
COVID-19	Coronavirus Disease 2019	
CRF	Case Report Form	
CSR	Clinical Study Report	
Diabetes Site	The site where the Investigator performs study follow	
Diabetes Site	up visits and diabetes management.	
DMR	duodenal mucosal resurfacing	
DSMB	Data Safety and Monitoring Board	
DTSQ	Diabetes Treatment Satisfaction Questionnaire	
EKG	Electrocardiogram	
	Estimated Glomerular Filtration Rate eGFR calculated	
eGFR	by Chronic Kidney Disease Epidemiology	
	Collaboration (CKD-EPI) Equation (2021)	
Endoscopy Site	The site where the Index Procedure is performed.	
FPG	Fasting Plasma Glucose	
GCP	Good Clinical Practice	
GI	Gastrointestinal	
GLMs	Glucose Lowering Medications	
HbA1c	Glycosylated Hemoglobin	
HDL	High-Density Lipoprotein	
HOMA-IR	Homeostatic Model Assessment of Insulin Resistance	
HIPAA	Health Insurance Portability and Accountability Act	
ICF	Informed Consent Form	
ICH	International Conference for Harmonization	
IDE	Investigational Device Exemption	

Abbreviation	Abbreviated Defined
I/E	Inclusion/Exclusion Criteria
IP	Investigational Plan
IRB	Institutional Review Board
ISO	International Organization for Standardization
ITT	Intent-to-Treat
LDL	Low-Density Lipoprotein
MedDRA	Medical Dictionary for Regulatory Activities
PP	Per Protocol
SAE	Serious Adverse Event
SAP	Statistical Analysis Plan
SU	Sulfonylurea
T2D	Type 2 Diabetes Mellitus
% TBWL	% Total Body Weight Loss
TIR	Time in range
UADE	Unanticipated Adverse Device Effect
ULN	Upper Limit of Normal

# 2. REVISION HISTORY

Version 1.0 of the Statistical Analysis Plan is the initial version of this document that has been released for production.

### 3. INTRODUCTION

This statistical analysis plan (SAP) describes the planned statistical methods to be used during the reporting and analysis of data collected under the Clinical Investigation Protocol entitled Safety and Feasibility of Endoscopic Application of a Novel Therapy for Duodenal Mucosal Regeneration in the Treatment of Type II Diabetes (REGENT-1-US Study), Doc. No. 346. This SAP should be read in conjunction with the study protocol and case report forms (CRFs).

The REGENT-1-US study is a multicenter, open-label, treatment-only study conducted in the United States. The study is designed to assess the feasibility and preliminary safety of the Endogenex device for endoscopic duodenal cellular regeneration in patients with type 2 diabetes (T2D) inadequately controlled on glucose-lowering medications. The protocol enrolled patients who were treated with non-insulin glucose-lowering agents; a tabulation of the treatment and number of patients is presented below.

Device Generation 1 / 600	Device Generation 1 / 600	Device Generation 2 / 750	All
Volts / Single Treatment	Volts / Double Treatment	Volts / Double Treatment	Patients
(n)	(n)	(n)	(n)
3	7	10	20

This plan is developed for analysis and reporting of the 48-week follow up data. The SAP may be revised in the future to address additional follow up data analysis beyond 48 weeks, if necessary.

Patients are considered enrolled in the study once the patient has passed endoscopic screening and proceeded to the Index procedure. *Screen failures* are defined as patients who consented to participate in the clinical study and started the screening tests specified by the protocol but are not subsequently enrolled into the study. Procedure success was defined as at least 6cm of duodenum was successfully treated.

The following analysis populations are defined for the presentation of the results from this study: *Intent-to-Treat* (ITT), *Full Analysis Set* (FAS) [referred to in the study protocol as the modified Intent-to-Treat (mITT) population], *Per-Protocol* (PP) and *Completed Cases* (CC). (Ref. Section 11.3 of the study protocol).

The primary and secondary safety analyses will be performed using the ITT population. The primary effectiveness analyses will be performed using the FAS population. The Per-Protocol population and Completed-Cases population will be used for the sensitivity analyses of the primary and secondary effectiveness endpoints.

*Intent-to-Treat*: The Intent-to-Treat population includes all enrolled patients, regardless of the patient having received the target treatment (at least 6cm of duodenum treated). The point of enrollment occurs when a patient has provided written informed consent and an energy delivery has been attempted during the index procedure.

*Full Analysis Set*: The FAS population consists of the ITT population patients who received the target treatment (at least 6 cm of duodenum treatment) and that have at least one post-treatment follow-up examination.

**Per-Protocol**: The Per-Protocol population is a subset of the FAS population and includes all patients who received the target treatment, do not have any major eligibility violations, and maintained stable glucose-lowering medications for 24 weeks post-procedure. The definition of what constitutes a major eligibility violations will be established before the study database is locked.

**Completed Cases**: The Completed Cases population is a subset of the Per-Protocol population and includes all patients who received the target treatment, do not have any major eligibility violations, and maintained stable glucose-lowering medications for 24 weeks post-procedure, and completed the final Week 48 End of Study Visit.

The details contained in this plan include the source code for the assessment of poolability across a myriad of factors and the analysis of each of the endpoints. Additionally, the structure of the table designs and a comprehensive index of the tables and listings has been provided.

This document contains information to support the generation of a Clinical Study Report (CSR). The planned analyses identified in this SAP may be included in regulatory submissions, medical presentations, and manuscripts. Exploratory analyses, not identified in this SAP, may be performed to support the clinical development program. Any post-hoc or unplanned analyses that are performed, but not identified in this SAP, will be clearly identified in the final report of the results. The structure and content of this SAP are designed to meet the requirements identified by the FDA and the International Conference on Harmonization (ICH) Guidance on Statistical Principles for Clinical Trials.

### 4. STUDY OBJECTIVES AND ENDPOINTS

# 4.1. Study Objectives

The objective of this first-in-human study is to assess the feasibility and preliminary safety of the Endogenex device for endoscopic duodenal cellular regeneration in individuals with type 2 diabetes inadequately controlled on glucose-lowering medications.

The study will also assess, treatment efficacy, evaluated by changes in glycemic control and liver enzymes following the study index procedure.

The primary objective of the study is to assess the safety of the Endogenex device.

The 3 secondary objectives, in order of presentation are as follows:

- To assess the technical feasibility of the Endogenex device for duodenal cellular regeneration
- To assess changes in glycemic control following the procedure
- To assess changes in liver enzymes following the procedure

(Ref. Section 3.0 of the study protocol)

# 4.2. Endpoints

There is a single primary endpoint predicated on safety and 18 secondary endpoints. The primary safety endpoint is the proportion of patients experiencing device-related or procedure-related serious adverse events within 12 weeks of the procedure.

For a complete presentation of safety, a tabulation of all adverse events over the course of the clinical investigation will be presented. Adverse events will be summarized as follows:

- All adverse events
- All procedure-related adverse events
- All device-related adverse events
- All serious adverse events
- All serious procedure-related adverse events
- All serious device-related adverse events
- All Unanticipated Adverse Device Effects (UADE)
- All Unanticipated Serious Adverse Device Effects (USADE)

The following elements (variable – label) will be presented in the supportive data listing (Ref. Case Report Form)

**AESEV** - Severity

- Mild
- Moderate

Version 1.0 Confidential Page 10 of 42

Severe

### AEOUT - Outcome

- Ongoing
- Resolved
- Resolved with sequalae
- Stabilized
- Death
- Unknown

### AEDREL - Relationship to Device

- Definitely related
- Possibly related
- Unlikely related

Not Related

AEPREL - Relationship to Procedure

- Definitely related
- Possibly related
- Unlikely related
- Not Related

AESER - Is this event a Serious Adverse Event?

- Yes
- No

### AESDTH - Led to death?

- Yes
- No

AESHOSP - Resulted in hospitalization (hospital stay >24 hours) or prolongation of an existing hospitalization?

- Yes
- No

AESLIFE - Led to life threatening illness or injury?

- Yes
- No

AESMIE - Required intervention to prevent life-threatening illness or injury or permanent impairment of a body structure or body function?

- Yes
- No

AESDISAB - Resulted in permanent impairment of a body structure or body function?

• Yes

• No

AESCONG - Led to fetal distress, fetal death or a congenital abnormality or birth defect?

- Yes
- No

AEUADE - Is this event considered by the investigator to be an UADE/USADE?

- Yes
- No

### 4.2.1. Secondary Endpoints

**First Secondary Endpoint:** Procedure success: defined as successful treatment of at least 6 cm of duodenum segment.

**Second Secondary Endpoint:** Procedure time: defined as the time between the Endogenex catheter insertion and the catheter removal.

Third Secondary Endpoint: Change from baseline (post-baseline minus baseline) in HbA1c reported for each pre-specified study visit.

Note: The estimates will be derived using a mixed model repeated measure procedure; the 24 week result will be the principal time point of interest.

**Fourth Secondary Endpoint:** Change from baseline (post-baseline minus baseline) in Fasting plasma glucose (FPG) reported for each pre-specified study visit.

Note: The estimates will be derived using a mixed model repeated measure procedure; the 24 week result will be the principal time point of interest.

**Fifth Secondary Endpoint:** Change from baseline (post-baseline minus baseline) in Insulinresistance by HOMA-IR reported for each pre-specified study visit.

Note: The estimates will be derived using a mixed model repeated measure procedure; the 24 week result will be the principal time point of interest.

**Sixth Secondary Endpoint Part 6a:** Change from baseline (post-baseline minus baseline) in Post-prandial plasma glucose (PPG) based on mixed meal tolerance test (MMTT) reported for each prespecified study visit.

Note: The estimates will be derived using a mixed model repeated measure procedure; the 12 week result will be the principal time point of interest.

**Sixth Secondary Endpoint Part 6b:** Change from baseline (post-baseline minus baseline) in beta cell function based on mixed meal tolerance test (MMTT) reported for each pre-specified study visit.

Note: The estimates will be derived using a mixed model repeated measure procedure; the 12 week result will be the principal time point of interest.

**Sixth Secondary Endpoint Part 6c:** Change from baseline (post-baseline minus baseline) in the disposition index based on mixed meal tolerance test (MMTT) reported for each pre-specified study visit.

Note: The estimates will be derived using a mixed model repeated measure procedure; the 12 week result will be the principal time point of interest.

**Seventh Secondary Endpoint:** o Time in range, glucose variability by continuous glucose monitoring (CGM)

**Eighth Secondary Endpoint:** Proportion of treated patients with an HbA1c improvement of ≥0.5% points from baseline at 24 weeks (24 week value minus the baseline value).

**Ninth Secondary Endpoint:** Proportion of treated participants with an HbA1c improvement of ≥0.5 points or more at 24 weeks from baseline and maintained at 48 weeks.

Note: Proportion of treated patients who achieve a HbA1c improvement of  $\geq 0.3\%$  or more at 24 weeks from baseline and maintained at 48 weeks. Patients who fail to maintain HbA1c improvement  $\geq 0.5\%$  at 48 weeks, for any reason, will be counted as not having achieved this endpoint. Patients who fail to achieve a HbA1c  $\geq 0.5\%$  improvement at 24 weeks will be excluded from the tabulation.

**Tenth Secondary Endpoint:** Change in weight from baseline (post-baseline minus baseline) by visit. Weight change will be reported in both kilograms and %TBWL.

Eleventh Secondary Endpoint: Change in glucose-lowering medication usage.

**Twelfth Secondary Endpoint:** Change in liver enzyme from baseline at 24 weeks (post-baseline minus baseline) for Alanine Aminotransferase (ALT).

**Thirteenth Secondary Endpoint:** Change in liver enzyme from baseline at 24 weeks (post-baseline minus baseline) for Aspartate Aminotransferase (AST).

Fourteenth Secondary Endpoint: Change from baseline in blood pressure by visit (systolic and diastolic run separately).

Fifteenth Secondary Endpoint: Change in lipid profile from baseline by visit: total cholesterol

Version 1.0 Confidential Page 13 of 42

Sixteenth Secondary Endpoint: Change in lipid profile from baseline by visit: triglycerides

Seventeenth Secondary Endpoint: Change in lipid profile from baseline by visit: HDL

Eighteenth Secondary Endpoint: Change in lipid profile from baseline by visit: LDL

# 4.2.2. Exploratory Endpoints

There are no exploratory endpoints.

### 5. STUDY OVERVIEW

## 5.1. Study Design and Description of the Study Device

This is a multicenter, open-label, treatment-only study conducted in the United States. A total of 20 participants is planned for the study. The study will test two treatment parameters. The first 10 participants will be treated at a generator setting of 600 Volts/ (600V) and the second group of 10 participants at 750 Volts/ (750V). In the 600V group, the first 5 participants will be enrolled/treated with the investigational device sequentially with at least 14 days observation time between each procedure. In the 750V group, the first participants will be enrolled/treated with the investigational device sequentially with at least 6 days observation time between each procedure.

Participants with T2D inadequately controlled on 2-3 non-insulin glucose-lowering medication(s) will be screened for study eligibility. Eligible participants who consent to participate in the study will maintain his/her background glucose-lowering medication(s) stable (no medication or dose change) for at least 12 weeks prior to baseline visit.

The index procedure will be performed under general anesthesia or deep sedation and within 21 days from the baseline visit. Participants will undergo endoscopic screening immediately prior to the DMR procedure, and eligible participants will undergo the DMR procedure. Participants may be discharged per local hospital's guideline; an overnight stay is not required but allowed per local policy and investigator's clinical judgement. A participant is enrolled in the study when the Endogenex catheter insertion is attempted. Participants excluded during endoscopic screening will be considered a screen failure and will be followed for four weeks after the procedure for safety.

Post index procedure, participants will be on a transitional diet consisting of clear liquids for 24 hours followed by a full liquid diet for 3 days, pureed food for 3 days, and soft food for one week, and then return to normal food as tolerated.

Background medication will be titrated to the pre-procedure dose and maintained for 24 weeks post index procedure and the transitional diet period per Section 6.2. After the 24-week follow-up visit, participants will be managed according to the current (2021) guidelines of the American Diabetes Association2 and their glucose-lowering medications will be optimized to achieve individualized A1c goals, which for most individuals is a target of less than 7.0%.

Participants will receive lifestyle-modification counseling sessions at scheduled intervals to promote adherence to a diet and lifestyle suitable for individuals with diabetes. Counseling will be provided by a member of the research team (endocrinologist, dietitian, nurse, etc.) trained in the delivery of lifestyle counseling for diabetes.

Participants will be followed up for 48 weeks after the index procedure. The primary endpoint will be evaluated at 12 weeks post procedure.

### 5.2. Schedule of Assessments

Reference Appendix 2. Schedule of Activities in the study protocol for the complete schedule of assessments.

## 5.3. Sample Size Justification

The study plans to enroll 20 participants and test two treatment parameters (600 volts and 750 volts), with 10 participants treated in each group. As this study is intended to characterize device safety and feasibility outcomes, formal sample size and power calculations based on hypothesis testing against a priori statistical objectives are not relevant; a sample size of 10 in each group and 20 in total is considered to be sufficient for the objectives of this investigation.

## 5.4. Estimated Duration of Patient Participation

Total duration on study will be calculated as the difference between the date of informed consent and the last on-study observation. All calculations defining the duration on study will be performed relative to the date of informed consent and follow the algorithm DURATION = ([STUDY COMPLETION OR WITHDRAW DATE – INFORMED CONSENT DATE])+1.

The first participant enrolled was in Q4, 2021; the estimated enrollment duration is 18 months.

### 6. ANALYSIS POPULATIONS

Patients will be considered enrolled in the study once the patient has passed endoscopic screening. Screen failures are defined as patient who consented to participate in the clinical study and started the screening tests specified by the protocol but are not subsequently enrolled in the study.

The primary and secondary safety analyses will be performed using the ITT. The primary effectiveness analyses will be performed using the FAS population. The Per-Protocol population and Completed-Cases population will be used for the sensitivity analyses of the primary and secondary effectiveness endpoints.

*Intent-to-Treat*: The Intent-to-Treat population includes all enrolled patients, regardless of the patient having received the target treatment (at least 6cm of duodenum treated). The point of enrollment occurs when a patient has provided written informed consent and an energy delivery has been attempted during the index procedure.

*Full Analysis Set*: The FAS population consists of the ITT population patients who received the target treatment (at least 6 cm of duodenum treatment) and that have at least one post-treatment follow-up examination.

**Per-Protocol**: The Per-Protocol population is a subset of the FAS population and includes all patients who received the target treatment, do not have any major eligibility violations, and maintained stable glucose-lowering medications for 24 weeks post-procedure. The definition of what constitutes a major eligibility violations will be established before the study database is locked.

**Completed Cases**: The Completed Cases population is a subset of the Per-Protocol population and includes all patients who received the target treatment, do not have any major eligibility violations, and maintained stable glucose-lowering medications for 24 weeks post-procedure, and completed the final Week 48 End of Study Visit.

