1.2 Duodenal Mucosal Resurfacing

The duodenum as a potential therapeutic target stems from evidence developed following bariatric surgeries. Surgical procedures involving bypassing a portion of the proximal intestine (such as Rouxen-Y Gastric Bypass, and Biliopancreatic Diversion) showed greater diabetes remission rate than gastric volume restrictive procedures such as sleeve gastrectomy, which implicates the important role of upper small intestine in blood glucose regulations.

Studies have found that the duodenal mucosa exhibits abnormal hypertrophy and endocrine hyperplasia in the presence of diabetes^{7,8}. It has been hypothesized that duodenal mucosal ablation followed by mucosal regeneration can improve glycemic control in T2D patients.

A duodenal mucosal resurfacing (DMR) procedure using hydrothermal ablation technique (Revita® DMR, Fractyl Laboratories, Lexington, MA., USA) has been studied in patients with T2D in a number of clinical trials. Rajagopalan et al⁹. reported results from 39 patients treated with DMR among 44 patients enrolled in a first-in-human study. Patients were 38 to 65 years old, had a mean diabetes duration of 5.7 years (0.2-9.7) and mean baseline hemoglobin A1c (HbA1c) of 9.5% (range 7.5% to 12%). Patients were required to be on at least one oral antidiabetic medications (OAD), 98% of them were on metformin and 37% on sulfonylurea before the procedure. The ablation length was between 3 and 15 cm of the post papillary duodenal mucosa. FPG reduction was noted within one week of the procedure and HbA1C reduction was observed as early as one month post intervention. HbA1C reduction was 1.2% at 6 months in the full cohort. Ablation length of ≥9 cm was associated with greater HbA1C reduction compared to shorter ablation length (1.4% vs. 0.7% at 6 months). The most common adverse event was transient, postprocedural abdominal pain that resolves without the need of analgesic medications. There was no gastrointestinal bleeding, perforation, pancreatitis, severe hypoglycemia, or evidence of malabsorption (i.e., calcium abnormalities or iron deficiency anemia).

Three patients developed a duodenal stenosis that presented as epigastric pain and vomiting 2–6 weeks after the procedure. They were successfully treated with endoscopic balloon dilation without sequelae. The authors attributed the cause of stenosis to early device and procedure issues that were improved subsequently.

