A subsequent study¹⁰ enrolled 46 patients, among them 37 completed the DMR procedure. Patients were 31-69 years old, 63% of them were male, had a mean BMI of 31.6 kg/cm2 and a baseline HbA1C of 8.6%. Improvements in HbA1c, FPG and HOMA-IR levels were observed as early as 4 weeks and sustained out to 12 months. Mean HbA1C reduction was 0.9% at 24 weeks, which was preserved up to 12 months. HOMA-IR was reduced by 2.9±1.1 at 24 weeks and by 3.3±0.9 at 12 months from baseline. The study also observed a statistically significant decrease in alanine transaminase (ALT) levels at 24 weeks and 12 months post procedure. Patients had a modest weight loss of 2.5kg at 24 weeks and 2.4 kg at 12 months. Most common study-related adverse events were GI symptoms. One study-related serious adverse event involved a patient with general malaise, mild fever (38°C), and increased c-reactive protein (CRP) level on the first day after DMR. The mild fever resolved within 24 hours and CRP level normalized within 3 days. No stenosis was reported in this study.

The above data supports the hypothesis that interventions targeting duodenal mucosa can improve glycemic control in T2D patients inadequately controlled by OAD. One limitation of hydrothermal ablation is the need to inject saline into the submucosal layer (mucosal lifting) during the ablation procedure for the purpose of preventing thermal penetration into deeper tissue. In addition to technical demand, mucosal lifting potentially creates an irregular contact surface between the ablation balloon and mucosa, resulting in uncontrolled and nonuniform ablation. One potential solution to address this limitation is to use a regeneration technology that does not require mucosal lifting.

[figure not shown]
Endogenex has developed a duodenal mucosal treatment device using a pulsed electric field (PEF) with bipolar pulse technology for the treatment of T2D. The treatment does not require mucosal lifting to protect muscularis from thermal damage, and therefore results in a simpler procedure and potentially more uniform tissue treatment.

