12.3 Analysis Populations

The following analysis populations are defined for the study: Intent-to-Treat (ITT), modified Intent-to-Treat (mITT), Per-Protocol (PP) and Completed Cases (CC). The primary safety analysis will be performed on the ITT population. The primary effectiveness analysis will be performed on mITT population.

- Intent-to-Treat: The Intent-to-Treat population includes all enrolled participants as defined in Section 5.3 regardless of whether or not the participant received the full treatment.
- Modified Intent-to-Treat: The mITT population consists of the ITT population participants who received the target treatment (at least 6 cm of duodenum treatment) and that have at least one post-treatment follow-up.
- Per-Protocol: The Per-Protocol population is a subset of the mITT population and includes all participants who received the target treatment (at least 6 cm of duodenum treatment), have at least one post-treatment follow-up, do not have any major eligibility violations, and maintained stable glucose-lowering medications for 24 weeks post procedure.

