### **Eighth Secondary Endpoint**

The distribution of this endpoint is binary. The analysis will be based on the proportion of patients that meet the endpoint at 24 weeks post-procedure. The primary population for analysis of this endpoint will be the FAS population.

Proportion of treated patients with an HbA1c improvement of  $\geq 0.5\%$  from baseline at 24 weeks (24 week score minus baseline score). Patients who fail to have HbA1c improvement of  $\geq 0.5$  points from baseline, for any reason, will be counted as not having achieved this endpoint.

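### No planned HbA1c, FPG or HOMA-IR analysis covers all enrolled patients: the FAS drops those with under 6 cm treated or no follow-up, and both sensitivity sets lie inside it

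*SAP*

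**What the plan says.** SAP Section 6 states: "The primary effectiveness analyses will be performed using the FAS population". Two conditions define that set. The first is treated length: "The FAS population consists of the ITT population patients who received the target treatment (at least 6 cm of duodenum treatment"). The second is follow-up: "and that have at least one post-treatment follow-up examination". The protocol calls the same set mITT and gives it the same role in Section 12.3: "The primary effectiveness analysis will be performed on mITT population". Protocol 12.4.4 adds a Per-Protocol analysis where appropriate.

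For sensitivity, SAP Section 6 says: "The Per-Protocol population and Completed-Cases population will be used for the sensitivity analyses of the primary and secondary effectiveness endpoints". Per-Protocol is defined there as a subset of the FAS, and Completed Cases as a subset of Per-Protocol. Both also require stable glucose-lowering medication for 24 weeks.

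The research questions in SAP 9.2 and the listed effectiveness tables (14.4.1 to 14.4.9) are for the FAS. For the 24-week HbA1c responder endpoint the SAP says: "The primary population for analysis of this endpoint will be the FAS population". It also says that failure for whatever reason counts as not achieved. Procedure success, the first secondary endpoint, is assigned to the FAS too.

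The primary safety endpoint is treated differently: SAP 9.1 analyses it on the ITT set and repeats it on the FAS and Per-Protocol sets.

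**The concern.** Both FAS conditions are settled after enrolment. A patient in whom 3 to 5 cm was treated has received energy. Protocol Appendix 2 schedules that patient for HbA1c at Weeks 4, 12, 24, 36 and 48 with no condition on treated length, and Protocol 8.2 does not list incomplete treatment as a reason to leave follow-up. The values should therefore exist, but no planned post-baseline HbA1c, FPG or HOMA-IR summary uses them.

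The protocol gives some reason to think that treated length matters. Section 1.2 reports of an earlier device: "Ablation length of ≥9 cm was associated with greater HbA1C reduction compared to shorter ablation length", with falls of 1.4% and 0.7% at 6 months.

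The responder endpoint has an additional problem. Its failure rule is strict, but the FAS restriction is applied first, so a short-treated patient leaves the denominator instead of counting as a failure.

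The groups in SAP Section 3 number 3, 7 and 10. One exclusion from the smallest removes a third of it, and unequal exclusions could distort the planned comparisons between groups.

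**Working it through.** **Plan's own figures.** The counts agree: 10 + 10 = 20 by voltage (Protocol 12.2, SAP 5.3) and 3 + 7 + 10 = 20 by treatment group (SAP 3). There is no power or precision calculation to reproduce.

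**Inputs.** Let k be the number of the 20 enrolled patients outside the FAS. It is not in the documents. For a rough range, Protocol 1.2 says of one earlier study that it "enrolled 46 patients, among them 37 completed the DMR procedure", so 9/46 = 19.6% did not complete. Another treated 39 of 44, so 5/44 = 11.4% were not treated. Scaled to 20 patients these give 3.9 and 2.3, hence k of about 2 to 4. The HbA1c falls of 0.9 (24 weeks), 1.4 and 0.7 also come from Protocol 1.2 and serve only as illustrations. The 60% FAS responder rate is an assumption.

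**Formulas.**
- All-enrolled mean fall = [(20 − k) × FAS mean + k × mean in those excluded] / 20.
- All-enrolled responder rate, with those excluded counted as not achieved = FAS rate × (20 − k) / 20.

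For k = 2: (18 × 0.90 + 2 × 0) / 20 = 0.81, and 60% × 18/20 = 54%.

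| k | Mean fall: FAS 0.90, excluded 0 | Mean fall: FAS 1.40, excluded 0.70 | Mean fall: FAS 0.90, excluded 1.40 | Responders: FAS 60%, excluded none |
|---|---|---|---|---|
| 0 | 0.90 | 1.40 | 0.90 | 60% |
| 1 | 0.855 | 1.365 | 0.925 | 57% |
| 2 | 0.81 | 1.33 | 0.95 | 54% |
| 4 | 0.72 | 1.26 | 1.00 | 48% |

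In the first scenario the FAS overstates the mean by 0.90/0.81 − 1 = 11% at k = 2 and by 0.90/0.72 − 1 = 25% at k = 4. In the third scenario the excluded patients do better and the sign reverses. If they do equally well, the means do not differ. For FAS responder rates from 40% to 80%, the gap is 4 to 8 points at k = 2 and 8 to 16 points at k = 4.

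**Which exclusion moves which estimate.** SAP 7.3.1 analyses observed data without imputation, dates aside. A patient with no follow-up has no change from baseline and adds nothing to a mean in either set; this exclusion can alter only a responder denominator. A short-treated patient with follow-up has values, so that exclusion can alter both.

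**Procedure success.** Success means at least 6 cm treated, and so does FAS membership. Within the FAS the rate is therefore 100% whatever happens. With 2 of 20 short-treated, the FAS gives 18/18 = 100% (exact 95% interval 81.5 to 100%), while all enrolled gives 18/20 = 90% (68.3 to 98.8%).

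**What counts as enrolled.** Protocol 5.3 and SAP 5.1 use attempted catheter insertion. SAP 6 opens with having passed endoscopic screening, then defines ITT by attempted energy delivery. SAP 10 defines ITT by initiation of endoscopic screening. These can give different denominators.

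**The case against.** The FAS is a disclosed choice, consistent between the two documents. The effect in patients who received the target treatment is a legitimate question in a 20-patient uncontrolled feasibility study. Protocol Section 3 calls efficacy exploratory, SAP 7.1 says testing is for information only, and the primary endpoint uses the ITT set. All of this stands, and it is why the FAS should remain the primary effectiveness set.

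A reader might infer that every glycaemic estimate is tilted toward benefit. The documents do not support that. It would need at least one excluded patient and worse outcomes in those excluded, and neither is given. The 1.4 versus 0.7 contrast comes from a different, hydrothermal device, is split at 9 cm and covers lengths of 3 to 15 cm. Its shorter group may include patients with 6 to 9 cm, who would be inside the FAS here. The completion fractions may also count enrolment differently, since endoscopic exclusions are screen failures in this trial.

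A reader might also infer that short-treated patients vanish from the results. They do not. Blood pressure by visit (SAP 8.7) and concomitant medication (SAP 11) are summarised on the ITT set. Patient accounting is by population (SAP 8.1), index procedure details are tabulated on the ITT set (SAP 8.4), and the laboratory listing carries population flags (SAP 8.5). With 20 patients the effect could be worked out by hand. That makes the gap smaller, but a listing is not a planned analysis.

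Finally, a general sentence in SAP Section 7 sends single-time results to ITT displays, which could be read as covering the responder endpoint and procedure success. The endpoint-specific text in SAP 9 and 9.2 says FAS, so the general sentence does not settle the matter.

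**Conclusion.** The gap is real and moderate, and it is confined to secondary endpoints. The bias toward benefit is possible, not shown: it requires k above 0 and a poorer outcome in those excluded. Under the assumption of no response in those excluded, the FAS overstates the mean HbA1c fall by 0.09 to 0.18 points (on 0.90) and the responder rate by 6 to 12 points (on 60%) for k of 2 to 4. If the excluded patients have half the effect, using 1.4 and 0.7, the mean gap is 0.07 to 0.14. At k = 0 all of these are zero.

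One consequence needs no assumption about outcomes: procedure success analysed on the FAS cannot be anything but 100%, so as planned it carries no information on technical feasibility.

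**What to change.** Keep the FAS as the primary effectiveness set and amend SAP Sections 6, 9 and 9.2 as follows.

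1. Settle one definition of enrolment and of the ITT set, and use it in SAP 3, 5.1, 6 and 10.
2. Add supportive ITT analyses of change in HbA1c, FPG and HOMA-IR, using all available values, including those from patients with under 6 cm treated.
3. Add an ITT version of the 24-week HbA1c responder endpoint, with a missing Week 24 value counted as not achieved.
4. Analyse procedure success on the ITT set.
5. Report the number excluded from the FAS, by treatment group and by reason.
6. Label FAS results *patients with at least 6 cm treated and follow-up*, not simply *treated patients*.

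The cost is SAP wording and one more set of tables from data already scheduled for collection. The reported figures may be slightly less favourable. If no enrolled patient falls outside the FAS, one sentence in the report saying so closes the point on the glycaemic endpoints.
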